1 STUDY SUMMARY

1.1 Synopsis

Title:	A Phase 1, Open-Label, Single Center, Dose Escalation Study of the Safety and Pharmacokinetics of mAb AZD5396 and mAb AZD8076 delivered as dMAbs in Healthy Adults
Short Title:	dMAbs for Prevention of COVID-19
Study Description:	
This is a Phase 1, open-label, single center, dose escalation study to evaluate the safety, tolerability and pharmacokinetic profile of mAb AZD5396 and mAb AZD8076 following delivery of optimized dMAb AZD5396 and dMAb AZD8076 with Hylenex® Recombinant, administered by intramuscular injection (IM) followed immediately by electroporation (EP) using the CELLECTRA™ 2000 with Side Port needle device, in a 2- to 4-dose regimen (Days 0, 3, 28, and 31) in healthy adults.
 
Our hypothesis is that the administration of dMAb AZD5396 and dMAb AZD8076 will be safe and associated with expression of mAb AZD5396 and mAb AZD8076 in serum.

Objectives:	
Primary Objectives:
 
 Describe the safety profile of all subjects in each study group Describe the pharmacokinetics of mAb AZD5396 and mAb AZD8076 (delivered by the administration of dMAb AZD5396 and dMAb AZD8076 with Hylenex® administered IM followed by EP with the CELLECTRA™ 2000 device). 
Exploratory Objective:
 
 To determine the antiviral activity of plasma of participants in the study when tested in an animal model of SARS-CoV-2 virus infection 28 days after the administration of dMAb AZD5396 and dMAb AZD8076. To evaluate the incidence of new SARS-COV-2 infection for the duration of the study

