Although antibodies can be highly effective for prevention of infectious diseases, they have limited prophylactic use due to biologic half-life and the complexities of IV administration. Monoclonal antibodies (mAbs) have a proven track record in the clinic for many years for antineoplastic, immunological indications and for the prevention and treatment of infectious diseases. However, to maintain protective levels of mAbs, repeated high dose bolus injections are required. For example, palivizumab (Synagis®), a recombinant mAb indicated for the prevention of serious lower respiratory tract disease caused by respiratory syncytial virus (RSV) in pediatric patients, not only requires dosing of subjects prior to beginning of the RSV season but also monthly thereafter throughout the active season to be effective. More recently, half-life extended mAbs with $t_{1/2}$ ranging from 70 to 130 days have been shown to be safe¹⁻³ and, nirsevimab, a high-potency RSV mAb has been shown to be effective in preventing RSV medically attended lower respiratory tract infections⁴. Additionally, production of recombinant mAb biologics in bioreactors is time intensive and costly, making their use prohibitive in low resource settings such as field clinics and during deployment, especially during a pandemic. Therefore, alternative approaches should be evaluated.

In practice, despite the EUA approval of monoclonal antibodies to treat and prevent COVID-19, hospitalization and death, this resource has been underutilized because of both logistical (number of available infusion beds and nurses able to administer the product) and supply constraints (enough availability of product). Intravenous mAb delivery can require several hours, and high doses for infusion and follow up are significant obstacles for quick administration. Additional solutions to deliver these life-saving biologics are needed.

2.1.6 *The dMAb Platform*

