4 STUDY PLAN

4.1 Study Design

This will be a Phase 1, open label, single center, dose escalation study to evaluate the safety, tolerability, and pharmacokinetic profile of mAb AZD5396 and mAb AZD8076 following delivery of optimized dMAb AZD5396 and dMAb AZD8076 with different doses of Hylenex® Recombinant, administered by intramuscular injection (IM) followed immediately by electroporation (EP) using the CELLECTRA™ 2000 with side port needle device, in a five-dose (8 cohort) regimen in healthy adults.

Up to 50 healthy volunteers 18 to 60 years of age will be enrolled in this study and evaluated across eight cohorts (n=3 to 6 per cohorts A1, A2, B, C, and D; n=5 per cohorts E, F, and G). Participants will be administered dMAb AZD5396 and dMAb AZD8076 at a five-dose level of each plasmid:

- 0.5 mg single-dose (cohort A1),
- 1 mg single-dose (cohort A2),
- 1 mg two-dose (cohorts B and F),
- 2 mg two-dose (cohort C),
- 0.25 mg two-dose (cohort D),
- 4 mg two-dose (cohort E), and
- 2 mg four-dose (cohort G).

Participants will receive two injections (one per dMAb) into the arm (deltoid)/leg (quadriceps) region at Day 0 alone (groups A1 and A2) or on day 0 and 3 (groups B-F) or on days 0, 3, 28, 31 (cohort G). Injections may be given in different arms or in an arm (deltoid) and a leg (quadriceps). If preferred or needed both doses can be done in the deltoid region or the lateral quadriceps, although the injections should be in different areas separated by at least 2 cm. The Day 3 injections may repeat an area already used on Day 0 as long as separated by at least 2 cm. The Day 31 injections may repeat an area already used on Day 28 as long as separated by at least 2 cm. The Day 28 injections may repeat an area already used on Day 0 or Day 3 injections with no separation required given the time span between injections.

This study will adhere to a dose escalation scheme as described in [Figure 2](#).

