D	dMAb AZD5396 and dMAb AZD8076	Day 0, 3	6 (3+3)	2x (0.25 mg dMAb AZD5396) + 2x (0.25 mg dMAb AZD8076)	34U	0.25 mL	OpBlock 0078	0.5 mg dMAb AZD5396 + 0.5 mg dMAb AZD8076
E	dMAb AZD5396 and dMAb AZD8076	Day 0, 3	5	2x (2 mg dMAb AZD5396) + 2x (2 mg dMAb AZD8076)	75U (0.5 mL)	0.70 mL	OpBlock 0078	4 mg dMAb AZD5396 + 4 mg dMAb AZD8076
F	dMAb AZD5396 and dMAb AZD8076	Day 0, 3	5	2x (0.5 mg dMAb AZD5396) + 2x (0.5 mg dMAb AZD8076)	75U (0.5 mL)	0.55 mL	OpBlock 0070	1 mg dMAb AZD5396 + 1 mg dMAb AZD8076
G	dMAb AZD5396 and dMAb AZD8076	Day 0, 3, 28, 31	5	4x (0.5 mg dMAb AZD5396) + 4x (0.5 mg dMAb AZD8076)	75U (0.5 mL)	0.55 mL	OpBlock 0078	2 mg dMAb AZD5396 + 2 mg dMAb AZD8076
	TOTAL		44-50^d					

^a All subjects will receive the study product by IM route of administration. All doses of optimized dMAb AZD5396 and dMAb AZD8076 will be prepared with Hylenex® less than 4 hours before dosing of subjects. Doses of Hylenex will vary depending on the cohort to allow for a different volume per injection

^b Use of CELLECTRA™ 2000 with Side Port needle, OpBlock 0078 and 5P-IM Side Port Array or Profusion Therapeutic Infusion needle (G47574) for Cohorts A-E & G.

^c Use of CELLECTRA™ 2000 with Side Port needle, OpBlock 0070 and 5P-IM Side Port Array for Cohort F.

^d Note that the n is defined as evaluable participants. Due to partial doses or early dropouts, we may dose up to 50 participants total to reach enough evaluable participants in each cohort. See Protocol section [8.2](#) which describes replacing participants.

The decision to open new cohorts in the clinical trial is justified by several key factors. Firstly, ensuring safety is of utmost importance in any clinical trial. By introducing additional cohorts, we will gather more data on the safety profile of the investigational product.

Secondly, evaluating the levels of expression of dMAbs is crucial for assessing the efficacy of this approach. The expression levels directly impact the therapeutic potency and effectiveness *in vivo*. By expanding the cohorts, we will gather a larger sample size and thereby obtain more reliable data on the expression levels of dMAbs in different individuals. This broader understanding of expression levels will aid in determining optimal dosages and predicting the treatment's potential success.

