Lastly, exploring different approaches to enhance the expression levels of dMAbs *in vivo* is a logical step forward. By opening new cohorts, we will introduce and test various strategies aimed at increasing the expression levels. These approaches may include novel delivery methods that will evaluate the tolerability of electroporation using alternative parameters and modified formulations. This exploration of different avenues increases the chances of finding innovative solutions to optimize the expression levels of dMAbs, potentially enhancing the treatment's efficacy and therapeutic impact.

In conclusion, opening new cohorts in the clinical trial is justified by the need to ensure safety, assess the expression levels of dMAbs, and explore diverse strategies to increase expression levels *in vivo*. This multifaceted approach strengthens the research process and provides a more comprehensive understanding of the investigational treatment, ultimately paving the way for improved therapeutic outcomes. The rationale for redosing participants with a DNA-encoded monoclonal antibody (dMAb) after 52 weeks is to evaluate the long-term efficacy and potential for sustained antibody presence in the system. This interval is strategically chosen based on the expected duration of dMAb-induced antibody production, hypothesizing that a yearly boost could reinforce the therapeutic effects.

[figure not shown]

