9.9 Serum Assessments

9.9.1 Pharmacokinetic Assessment

Serum samples will be collected at baseline (Day 0), on Day 3, Day 28 (cohort G), Day 31 (cohort G) prior to dosing, and at all subsequent visits (including unscheduled visits in the event that serum mAb AZD5396 and mAb AZD8076 are detected at the Day 42 (Week 6) visit). Blood will be collected for serum at each specified visit. Details on the process for serum sample collection, storage, and shipment will be provided in the Laboratory Manual. Serum samples will be evaluated to determine the expression kinetics (i.e., pharmacokinetics) of mAb AZD5396 and mAb AZD8076 upon Investigational product administration. The serum concentration–time profile of mAb AZD5396 and mAb AZD8076 (ng/mL) will be evaluated for each participant using all available time points. The maximum serum concentration (C_{max}), the minimum serum concentration (C_{min}), and the Area Under the Curve (AUC_{0-t}) in the course of the study will be calculated as the data allows. Assays to quantitatively determine mAb AZD5396 and mAb AZD8076 levels in human serum samples are currently under development and will include either a mass spectrometry assay and/or a Meso Scale Discovery (MSD) Electrochemiluminescence (ECL) assay that will be qualified for its intended purpose using the FDA Bioanalytical Method Validation Guidance for Industry as a reference.

Serum Pharmacokinetic Assay Description

A validated assays for quantification of serum concentrations of AZD5396 and mAb AZD8076 will be carried out, using the assay previously developed to assay PK of AZD1061 and AZD8895, respectively.

To measure the AZD7442 (AZD1061 and AZD8895) human serum concentration, an immunoaffinity enrichment using streptavidin magnetic beads coated with biotinylated RBD of SARS-CoV-2 followed by LC-MS/MS approach was used. Because AZD8895 and AZD1061 are too large for practical direct quantitative analysis using LC-MS/MS technology, the captured proteins are subjected to “on-bead” proteolysis with trypsin, following standard protein denaturation, reduction, and alkylation processing steps. As a result of the trypsin digestion, characteristic peptide fragments originating from AZD8895 and AZD1061 are produced. The characteristic peptides are quantified as surrogates for the AZD8895 and AZD1061 serum concentrations.

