11.3.2 Pharmacokinetic Analyses

The number and percentage of participants in which detection of monoclonal antibody mAb AZD5396 and mAb AZD8076 in serum is achieved will be summarized with a point estimate and corresponding

exact 90% Clopper-Pearson confidence interval. These will be summarized per time point within each cohort. We will also estimate the time to 50% decline from peak concentration.

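### Section 4.1 justifies redosing at 52 weeks, but the only second course is Cohort G's on Days 28 and 31, and the whole-study PK summaries do not separate that course from the first

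*Protocol*

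**What the plan says.** **Rationale.** The closing paragraph of section 4.1 says "The rationale for redosing participants with a DNA-encoded monoclonal antibody (dMAb) after 52 weeks is to evaluate the long-term efficacy", and continues: "This interval is strategically chosen based on the expected duration of dMAb-induced antibody production, hypothesizing that a yearly boost".

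**Schedule.** The synopsis describes dosing "in a 2- to 4-dose regimen (Days 0, 3, 28, and 31". Section 4.1 places the injections on Day 0 alone (A1, A2), on Days 0 and 3 (B to F), or "on days 0, 3, 28, 31 (cohort G". Table 2 gives Cohort G as "4x (0.5 mg dMAb AZD5396) + 4x (0.5 mg dMAb AZD8076" with n=5. Table 4 marks inoculation on Days 0, 3, 28 and 31 only, and sections 7.3 and 9.5 agree. Section 7.6 lists Week 52 among the assessment visits, with no administration.

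**PK summaries.** Section 9.9.1 says that Cmax, Cmin and AUC0-t "in the course of the study will be calculated as the data allows". Section 11.3.2 summarises detection per time point within each cohort and adds: "We will also estimate the time to 50% decline from peak concentration". Neither section distinguishes Cohort G's first course from its second.

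**Sampling.** Section 9.9.1 schedules serum before dosing on Days 28 and 31 in Cohort G and at all later visits, and evaluates each participant's concentration-time profile.

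**The concern.** There are two separate problems.

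First, the protocol states a purpose that the design does not have. A reader of section 4.1 would expect a 52-week redose and evidence on annual boosting. The design gives neither, and it does not say what the 28-day redose is meant to show.

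Second, the PK summaries suit a single course. In Cohort G the second course starts while first-course antibody is probably still circulating. One Cmax per participant may belong to either course. One AUC adds them together. A whole-study Cmin need not be the level just before the second course. A decline timed from the peak depends on which peak is meant. Detection after Day 28 can be positive from the first course alone. What is at stake is whether the reported tables show what the second course contributed.

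**Working it through.** The protocol gives no figure for the redosing question, so there is none to reproduce. The check sets the passages side by side and then sizes the carry-over.

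**1. Interval.** The stated interval is 52 weeks, or 52 × 7 = 364 days. The actual interval between course starts is 28 days (Day 0 to Day 28). The last dose in any cohort is on Day 31.

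**2. Is carry-over plausible?**
- Section 2.2.2: in macaques given these products, antibody was detectable for up to 49 days after the last dose, which is longer than 28 days.
- Section 2.1.3: the parent antibodies carry the YTE half-life extension. Section 2.1.4 names reversion of TM as the only difference, so YTE appears to be retained.
- Section 2.1.5 cites half-lives for other half-life-extended antibodies "ranging from 70 to 130 days have been shown to be safe". This is a class figure; none is given for the study antibodies. I therefore treat 70 and 130 days as assumptions and add 21 days as a deliberately short one.

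**3. Fraction of a declining level left after 28 days**, f = 2^(−28/t½):

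| Assumed t½ | f |
|---|---|
| 21 days | 2^(−28/21) = 0.397 |
| 70 days | 2^(−28/70) = 0.758 |
| 130 days | 2^(−28/130) = 0.861 |

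**4. Effect on whole-study Cmax and AUC.** Let r be second-course expression relative to the first, with both courses taking the same time to peak. Relative to one course alone, Cmax is max(1, f + r) and AUC is about 1 + r.

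| r | Cmax, t½ 21 d | Cmax, t½ 70 d | Cmax, t½ 130 d | AUC |
|---|---|---|---|---|
| 0 | 1.00 | 1.00 | 1.00 | 1.00 |
| 0.25 | 1.00 | 1.01 | 1.11 | 1.25 |
| 0.5 | 1.00 | 1.26 | 1.36 | about 1.5 |
| 1 | 1.40 | 1.76 | 1.86 | about 2.0 |

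A model with 14 or 28 days of constant expression and half-lives of 70 to 130 days gives nearly the same Cmax ratios. With 56 days of expression, r = 0.25 gives 1.14 to 1.15. A weak second course therefore moves whole-study Cmax little, while a fully effective one moves it clearly.

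**5. Can another cohort supply the single-course reference?** Only imperfectly. Cohort B shares G's 0.5 mg per injection and OpBlock 0078, but has 66.5U Hylenex in 0.5 mL against 75U in 0.55 mL. Cohort F shares dose, Hylenex and volume, but uses OpBlock 0070.

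**6. Detection.** If all five Cohort G participants are positive at a visit after Day 28, the exact 90% interval runs from 0.05^(1/5) = 0.549 to 1.00, whichever course the antibody came from.

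**7. Does the Day 28 pre-dose sample help?** In a declining phase, the first-course level 14 days later is 2^(−14/70) = 0.871 to 2^(−14/130) = 0.928 of the Day 28 level (0.630 at 21 days). A rise above Day 28 would then point to the second course. The limit is prolonged expression: in the 56-day model the Day 28 level is only 51% to 55% of the first-course peak. The first course alone could then carry it to about 1/0.55 = 1.8 to 1/0.51 = 2.0 times Day 28. The trend over Week 2, Week 3 and Day 28 shows which case applies.

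**The case against.** The strongest reply is that only the 52-week paragraph is wrong, and that it alters no dose, visit, sample or endpoint. It does not name Cohort G and closes a general case for opening new cohorts. That is fair as to the link with G, which is an inference. But G is the only cohort with a second course, so the paragraph describes either G wrongly or a redose that does not exist.

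The second reply is that splitting parameters by course is detail for a statistical analysis plan, which was not among the documents reviewed and may do so. That limits the weight of the PK point. It does not remove it, because the protocol itself fixes the window as the whole study and refers to one unnamed peak.

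A reader might go further and infer that Cohort G cannot answer any redosing question, or that a failed redose would pass for sustained expression. The documents do not support this. Pre-dose samples, individual profiles and per-visit detection are all planned, and anti-drug antibody is drawn alongside PK. A profile with no rise after Day 28 would be visible.

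Nor can one say how long carry-over would keep participants detectable. That needs Day 28 concentrations, which are not given, and a known assay floor. The 0.300 to 30.0 µg/mL range in section 9.9.1 belongs to the parent-antibody method, and the same section says that assays are still under development.

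**Conclusion.** The contradiction is certain: 52 weeks in the rationale, 28 days in every schedule, and no dose after Day 31. No evidence on a yearly boost can come from this trial, and the interval actually used has no stated reason.

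The PK point holds in a limited form. As defined, Cmax, Cmin, AUC0-t and the decline from peak do not isolate Cohort G's second course. Carry-over of roughly 40% to 86% of a declining level after 28 days rests on assumed half-lives of 21 to 130 days, not on a value for these antibodies. The fault lies in how the summaries are defined. The sampling is adequate, and the Day 28 redose question remains answerable, descriptively, in five participants.

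**What to change.** 1. Reconcile the last paragraph of section 4.1 with Table 2, Table 4 and section 7.3. Which interval is intended is for the sponsor to state. If the present schedule stands, remove the yearly-boost and long-term-efficacy statement and say what question the Day 28/31 redose addresses.
2. In sections 9.9.1 and 11.3.2, define Cohort G's PK by course. Course 1 runs from Day 0 to the Day 28 pre-dose sample. Course 2 runs from Day 28 onward, reported as increment and ratio over the Day 28 pre-dose level, next to the Week 2 to Day 28 trend.
3. Time the 50% decline from a named, course-specific peak.
4. State that detection after Day 28 is not by itself evidence of second-course expression.

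The cost is a few sentences and one small table for five participants. No sample or visit is added.

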4.2 Dose Escalation Scheme

The study will apply a single ascending dose (SAD) modified 3+3 design. This study will adhere to a dose escalation scheme as described in [Figure 2](#). Participants will be enrolled sequentially beginning with Cohort A1. The first participant in cohort A1 will be dosed on Day 0 following confirmation of eligibility criteria. If no stopping event (DLT) is observed (see [Section 10.10](#)) after 14 days of the initial dose, the remaining two participants in that cohort will be dosed. If there are 0 DLT events after 14 days of the initial dosing of the third subject, enrollment will be completed, and then cohort A2 will open. Same process will be followed for cohorts B and C. Because cohorts D, F, & G are a similar or lower dose and the safety profile would have been already established in previous cohorts, the 14-day waiting periods will not apply to Cohorts D, F, or G. Even though the levels of expression observed in cohorts

A-D are way below the levels seen when the monoclonal antibodies are given as protein, Cohort E will receive a higher dose which will require a 14 day waiting period after the dosing of the first participant at this level. Every participant in Cohort E following the 14 day waiting period will be dosed 3 days apart as in other cohorts.

If one dose limiting toxicity (DLT) is observed in the first three participants enrolled in any cohort, an ad hoc DSMB will review the event and make a decision if the study should continue. If the DSMB agrees that the study should continue, the remaining participants will be enrolled in the cohort and dosed but the next cohort will not open until the 28-day period of safety is completed. However, if any additional DLT occurs (i.e., >1 DLT in 6 total participants in a given cohort), then that dose will be deemed not tolerated.

Figure 2. Dose Escalation Scheme

Doses of Investigational product will be administered intramuscularly in ~0.5 mL/dose volume in cohorts A1, B, F, & G; ~1 mL/dose volume in cohorts A2 & C; ~0.25 mL/dose volume in cohort D; and ~2 mL/dose volume in cohort E, followed immediately by EP with the CELLECTRA™ 2000 with Side Port needle device. It is recommended that the investigational product be administered such that the injection is delivered slowly using the side port needle in muscle. The side port needle should be fully

inserted prior to the injection, held in place for a moment, then removed prior to EP. Firm pressure should be used to complete injection and then the needle removed prior to EP.

Safety will be reviewed by the DSMB. Progression to the next cohort is dependent on an acceptable safety profile of all 3, 5, or 6 participants completing, at a minimum, the Day 14 after the first dose, except for Cohort D (or 28 days after the last dose, if DLT observed). Following the first review, all subsequent reviews will include data from all enrolled participants.

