Participants will be enrolled sequentially beginning with Cohort A1. The first participant in cohort A1 will be dosed 0.5 mg of each product once on Day 0 following confirmation of eligibility criteria. If no stopping event (DLT) is observed (see Section [10.10](#)) after 14 days of the initial dose, the remaining two participants in that cohort A1 will be dosed three days apart. If there are 0 DLT events after 14 days of the initial dosing of the third subject, cohort A2 will open and will follow the same schedule. Same process will be followed for the next cohorts with a total of 6 participants enrolled in each of cohort B to C (See [Figure 2](#)), 1 sentinel participant will be enrolled initially and, after 14 days of observation, the additional 5 participants will be enrolled three days apart each. If there are 0 DLT events past 14 days after the initial dosing of the last participant, the next cohort will open. Because cohorts D F, & G are a similar or lower dose and the safety profile have been already established in previous cohorts, the 14-day waiting periods will not apply to Cohorts D, F, or G. Even though the levels of expression observed in cohorts A-D are way below the levels seen when the monoclonal antibodies are given as protein, Cohort E will receive a higher dose which will require a 14 day waiting period after the dosing of the first participant at this level. Every participant in Cohort E following the 14 day waiting period will be dosed 3 days apart as done in other cohorts. Any DLT will be reported to the FDA in an expedited manner.

Table 2. Dosing Arms and Regimens

Cohort	Study Product	Dose Schedule	n	No. injections per dose (dose formulation in mg) 2 injections are given on each day	Hylenex dose per injection	Final volume per injection	EP parameters	Total dose of each dMAb (mg)
A1	dMAb AZD5396 and dMAb AZD8076	Day 0	3	1x (0.5 mg dMAb AZD5396) + 1x (0.5 mg dMAb AZD8076)	68U	0.5 mL	OpBlock 0078	0.5 mg dMAb AZD5396 + 0.5 mg dMAb AZD8076
A2	dMAb AZD5396 and dMAb AZD8076	Day 0	3	1x (1mg dMAb AZD5396) + 1x (1 mg dMAb AZD8076)	135U	1 mL	OpBlock 0078	1 mg dMAb AZD5396 + 1 mg dMAb AZD8076
B	dMAb AZD5396 and dMAb AZD8076	Day 0, 3	6 (3+3)	2x (0.5 mg dMAb AZD5396) + 2x (0.5 mg dMAb AZD8076)	66.5U	0.5 mL	OpBlock 0078	1 mg dMAb AZD5396 + 1 mg dMAb AZD8076
C	dMAb AZD5396 and dMAb AZD8076	Day 0, 3	6 (3+3)	2x (1 mg dMAb AZD5396) + 2x (1 mg dMAb AZD8076)	135U	1 mL	OpBlock 0078	2 mg dMAb AZD5396 + 2 mg dMAb AZD8076

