7.2 Dosing and Follow-Up Evaluations

Once eligibility has been confirmed, the participant will be assigned to receive Investigational product. Visit dates and windows must be calculated from Day 0.

7.3 Day 0, Day 3, Day 28, and Day 31

The following evaluations will be performed on Day 0 (all cohorts), Day 3 (cohorts B-G), Day 28 (cohort G), and Day 31 (cohort G) only prior to Investigational product administration:

- Collect all present and/or new or ongoing adverse events (including history of new COVID 19 diagnosis).
- Document any present conditions and concomitant illnesses.
- Record current concomitant medications/treatments.
- Targeted physical examination (driven by symptoms).
- Record vital signs pre injection including heart rate (HR), respiratory rate (RR), blood pressure (BP), oral temperature.
- Collect urine for urinalysis and urine pregnancy test (if WOCBP).
- Collect blood for PT(INR) and aPTT, CBC with differential, serum chemistry, CPK.
- Collect serum for mAb AZD5396 and mAb AZD8076 level assessment and ADA evaluation.
- Provide Memory Aid.

Investigational product administration should occur after all the above pre-dose procedures have been completed.

Participants will receive two injections into the arm (deltoid)/leg (quadriceps) region at day 0 (all groups), and on day 3. Injections will be separated by ~30 minutes. Injections may be given in different arms or in an arm (deltoid) and a leg (quadriceps). If preferred or needed both doses can be done in the deltoid region or the lateral quadriceps, although the injections should be in different areas separated by at least 2 cm. The Day 3 injections may repeat an area already used on Day 0 as long as separated by at least 2 cm. For Cohort G, the Day 28 injections may be repeated in an area already used, and the Day 31 injections may repeat an area already used on Day 28 as long as separated by at least 2 cm.

If a participant has a DLT, as outlined in the protocol, the second dose of the product will not be given.

The following evaluations will be performed on Day 0 (all cohorts), Day 3 (cohorts B-G), Day 28 (cohort G), and Day 31 (cohort G) after Investigational product administration:

- Conduct targeted injection site reaction systemic and local assessments 30 min post each injection.
- Record vital signs post each injection including heart rate (HR), respiratory rate (RR), blood pressure (BP), oral temperature. Participants will be observed for 1 hour after the last injection.

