10.10 Dose Limiting Toxicity Criteria

Dose limiting toxicities are defined below for the purposes of evaluating the safety of the administered doses of dMAb AZD5396 and dMAb AZD8076. The following Investigational product administration-and/or EP- related adverse events are defined as DLTs:

- Grade 3 or greater local injection site erythema, swelling, and/or induration recorded \geq 1 hour after Investigational product administration
- Pain or tenderness at the injection site that requires overnight hospitalization despite proper use of non-narcotic analgesics.

- Grade 3 or greater systemic symptoms assessed by the Principal Investigator as related to Investigational product administration.
- Grade 3 or greater clinically significant laboratory abnormalities assessed by the Principal Investigator as related to Investigational product administration.

The most severe grade for that particular event is to be documented on the CRFs for DLT.

DLT assessment is scheduled for the first 3 to 6 participants for specified cohorts at Day 14 (Week2). Study Investigators are required to conduct clinical assessment and review blood test results performed. The DSMB is responsible for reviewing available safety data for specified cohorts. Refer to Section [4.2](#) for additional information on DLTs and the dose escalation scheme.

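### Cohort E: participants 4 and 5 are nominally fully dosed before participant 3's Day 14 DLT assessment, and a first DLT in participant 4 does not trigger the section 4.2 review

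*Protocol*

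**What the plan says.** Protocol section 4.2 sets the trigger: "If one dose limiting toxicity (DLT) is observed in the first three participants enrolled in any cohort", an ad hoc DSMB decides whether the study goes on. If it agrees, "the remaining participants will be enrolled in the cohort and dosed but the next cohort will not open" until a 28-day safety period is complete.

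Cohort E has "n=5 per cohorts E, F, and G" (section 4.1) and receives 4 mg of each dMAb in total, twice the total of Cohort C (Table 2). Section 4.1 says that "Cohort E will receive a higher dose which will require a 14 day waiting period after the dosing of the first participant". After that wait, section 4.2 states: "Every participant in Cohort E following the 14 day waiting period will be dosed 3 days apart as in other cohorts". Neither section adds a pause after participant 3.

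Section 10.10 places the DLT assessment at Day 14 for the first three to six participants of specified cohorts. Its DLT list includes "Grade 3 or greater clinically significant laboratory abnormalities assessed by the Principal Investigator as related to Investigational product administration". Under section 7.3, "If a participant has a DLT, as outlined in the protocol, the second dose of the product will not be given"; this concerns the affected participant only. The Day 14 condition at the end of section 4.2 governs the opening of the next cohort, not dosing within the current one.

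**The concern.** A review that decides whether the remaining participants are dosed is useful only if some of them still have doses to come when the DLT becomes known. In Cohort E the remaining participants are numbers 4 and 5, and the 3-day spacing brings their doses forward of most of the follow-up of participants 2 and 3. A laboratory DLT after a second dose would first show at the Day 7 tests, and the scheduled assessment comes a week after that.

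The trigger also stops at the third participant. If the first DLT occurs in participant 4, section 4.2 calls for no review, although participant 5 may still have a dose due. At stake is further exposure of healthy volunteers at the highest dose, in the one late cohort for which the protocol itself saw a need to wait.

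**Working it through.** The plan states no figure on this point, so the check is a calendar count from its own intervals.

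**Inputs.** Cohort size 5 (4.1). Doses on Day 0 and Day 3 (4.1, Table 2). A 14-day wait after participant 1, then 3-day spacing (4.1, 4.2). Safety laboratory tests before the Day 3 dose, at Day 7 and at Day 10 (7.3 to 7.5). DLT assessment at Day 14 (10.10). Day 3, 7 and 10 windows of 1 day either way and a Week 2 window of 2 days either way (Table 3).

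**Calendar.** T is the number of days from the sentinel's first dose, on the earliest permitted schedule. The first dose of participant k (k = 2 to 5) is at T = 14 + 3(k − 2); the second is 3 days later.

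| Participant | First dose | Second dose | Day 7 | Day 10 | Day 14 |
|---|---|---|---|---|---|
| 1 | 0 | 3 | 7 | 10 | 14 |
| 2 | 14 | 17 | 21 | 24 | 28 |
| 3 | 17 | 20 | 24 | 27 | 31 |
| 4 | 20 | 23 | 27 | 30 | 34 |
| 5 | 23 | 26 | 30 | 33 | 37 |

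**Visits still open.** The dosing visits of participants 4 and 5 are at T20, T23, T23 and T26. The number later than each assessment is:

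| Assessment | T | Open, of 4 |
|---|---|---|
| Participant 2, Day 3 pre-dose tests | 17 | 4 |
| Participant 3, Day 3 pre-dose tests | 20 | 3, plus participant 4's first dose the same day |
| Participant 2, Day 7 | 21 | 3 |
| Participant 3, Day 7 | 24 | 1 (participant 5's second dose) |
| Participant 3, Day 10 | 27 | 0 |
| Participant 2, Day 14 | 28 | 0 |
| Participant 3, Day 14 | 31 | 0 |

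Across the visit windows, participant 3's Day 7 leaves 0 to 2 visits. Participant 2's Week 2 visit leaves 0, or 1 at the extremes, and participant 3's Week 2 visit always leaves 0. If results took 2 days (an assumption; no turnaround is given), participant 3's Day 7 result would arrive at T26, the day of the last dose. Starting participant 2 later shifts all later dates together and leaves the counts for participants 2 and 3 unchanged.

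**Participant 4.** The Day 7 tests (T27) come after participant 5's last dose (T26). Only a DLT seen by T26 leaves anything to hold, and section 4.2 calls for no review of it.

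**How often, at most.** Let p be the true DLT rate and q = 1 − p, with participants independent and at equal risk. Section 11.4 uses 30% as its target DLT estimate; 10% and 20% are assumed for the range.

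- First DLT in participant 3, q²p: 0.9² × 0.1 = 0.081; 0.8² × 0.2 = 0.128; 0.7² × 0.3 = 0.147.
- First DLT in participant 4, q³p: 0.9³ × 0.1 = 0.073; 0.8³ × 0.2 = 0.102; 0.7³ × 0.3 = 0.103.

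Both rows count every DLT. The first includes those seen early enough to stop dosing, and the second includes those seen too late for any hold to matter. They are therefore upper bounds for these two routes, and the relevant fraction is unknown. A first DLT in participant 2 is not in these figures; at that participant's Day 7 tests, 3 of 4 visits are still open.

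**The case against.** The strongest reply is that this is a choice of stagger, not a contradiction. The trigger applies to a DLT that has been observed; section 4.2 nowhere promises that participants 4 and 5 wait for participant 3's Day 14. Section 4.1 describes the same pattern, one sentinel and then 3-day spacing, for Cohorts B and C. The sentinel passes through both doses and the Day 7, 10 and 14 assessments before anyone else is dosed, so the late-laboratory route is covered once. No staggered scheme excludes a DLT found late. That stands, and it makes the length of the stagger a matter of judgement.

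Other safeguards also act. Section 10.11 pauses the trial for any SAE, any potentially life-threatening or unexpected Grade 4 event, anaphylaxis, DLTs in two thirds of a cohort, or two Grade 3 or higher events of the same kind or organ class across all cohorts. The DSMB reviews all DLTs (14.2.1) and may recommend stopping enrolment at any time (11.3.5). These narrow the gap, but none is an automatic hold after one isolated, non-serious Grade 3 DLT.

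A reader might infer that two volunteers would receive the highest dose after participant 3 has already had an unmeasured DLT. The schedule does not support that in full. Participant 3's second dose and participant 4's first dose fall on the same day, T20. For a DLT caused by the second dose, what follows is participant 4's second dose and participant 5's two doses. A DLT caused by the first dose can be seen clinically or in the Day 3 pre-dose tests.

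Figure 2 and the DSMB charter are not available here and might contain a hold. The trigger and the spacing are both in the text of section 4.2, which mentions none.

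**Conclusion.** The point holds in a limited form. On the nominal schedule, participants 4 and 5 of Cohort E have had all four dosing visits before participant 3's Day 14 DLT assessment, and 1 of 4 (0 to 2 across windows) is open at participant 3's Day 7 tests. A first DLT in participant 4 does not trigger the section 4.2 review.

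The exposed case is an isolated, non-serious Grade 3 DLT found late, mainly a laboratory one after the second dose, in participant 2 or 3; or any such first DLT in participant 4 while participant 5 still has a dose due. The 8% to 15% (participant 3) and 7% to 10% (participant 4) are upper bounds and do not measure the gap itself.

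It would be too strong to say that the DSMB step is without effect in Cohort E. Clinical DLTs in the first days, the Day 3 pre-dose tests and participant 2's Day 7 tests can still stop some dosing. Nor does the cohort size of five leave the rejection rule undefined: two DLTs in five already reject the dose, so the wording about more than one DLT in six needs no change.

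The counts assume the earliest permitted schedule, that Cohort E is among the cohorts meant in section 10.10, and, in the plan's favour, that a DSMB review would also hold second doses already due.

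**What to change.** **Main change, in section 4.2.** State that a first DLT in any participant of a cohort holds all further first and second doses in that cohort until the DSMB has decided. This brings participant 4 within the rule and makes clear that second doses are included. It costs nothing unless a DLT occurs. Alone, it cannot act on a DLT not yet found, so the count of 1 of 4 at T24 stays.

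**Preferably also, for Cohort E.** Do not dose participants 4 and 5 until participants 1 to 3 have completed the Day 14 assessment and their laboratory results have been reviewed. Participant 4 would then be dosed at T31 and T34, and participant 5 at T34 and T37. All four visits could be held for a DLT found in participant 3 up to T31, provided that participant 4 is dosed after that day's review. Participant 5 would still follow participant 4 by 3 days, which the main change covers for a DLT seen by then.

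The second change costs 31 − 20 = 11 days plus laboratory turnaround, and possibly rescreening if the 30-day screening window lapses for participant 4 or 5. It adds no participants and no scheduled visits. It is more a matter of judgement than the first.
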